5.4. Adjustment for Covariates

No adjustment for covariates will be performed.

5.5. Handling of Dropouts and Missing Values

5.5.1. Anti-fXa Activity

For patients treated with apixaban, rivaroxaban, and edoxaban, anti-fXa values greater than 950 ng/mL the anti-fXa value will be replaced with 950. If the anti-fXa value is < 4.0 ng/mL then the value will be replaced with 4.0. For enoxaparin treated patients, anti-fXa values identified as < 0.10 IU/mL will be replaced with 0.10.

If the baseline anti-fXa activity is missing, the patient will be excluded from the efficacy analysis population. For post baseline assessments, if both the EOB and EOI assessments are missing, the maximum change will be replaced with zero (i.e., no change from baseline) and the Nadir will be replaced with the baseline value using the Baseline Observation Carried Forward principle (BOCF principle). If only one post-baseline sample is missing, the available sample (either EOB or EOI) will be used for the imputation (Last Observation Carried Forward [LOCF]).

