11.5.6. Statistical Methodology for Endpoint Analyses

The first primary efficacy endpoint, i.e., percent change in anti-fXa activity from baseline (last measurement before administration of andexanet) to nadir (the lowest level measured between 5 minutes prior to the start of andexanet administration and 10 minutes after the end of the andexanet administration) will be calculated for each patient as change = 100 %×(post-baseline)/baseline. Percent change from baseline in anti-fXa activity will be assessed with two-sided 95% CIs. A nonparametric CI for the median will be reported. If the nonparametric CI for the median excludes 0, the first primary objective will be considered to have been met. For the first primary endpoint, patients who do not have at least one anti-fXa activity level within the evaluation period for non-administrative reasons will have percent decrease imputed as 0.0% (i.e., using the baseline value as the nadir value).

The second primary efficacy endpoint, proportion of efficacy evaluable patients who are adjudicated to have effective hemostasis (excellent or good) by the independent EAC will be summarized as a point estimate with an asymptotic 95% confidence interval.

To maintain the type I error rate, the statistical evaluation of the primary endpoints, including the analysis of hemostatic efficacy in specific study populations against specific comparators, will be ordered in a fixed sequence multiple comparisons (hierarchical) procedure.

The secondary endpoint will be assessed by plotting the Receiver Operating Characteristics (ROC) curve and calculating the Area Under the Curve (AUC). Patients will be classified as success or failure based on achievement of hemostatic efficacy. For each potential cut point of a percent change in anti-fXa activity, the sensitivity and specificity of that cut point to distinguish achievement of hemostatic efficacy will be calculated. The ROC plots sensitivity by 1 - specificity. An AUC of 0.5 or lower indicates that the percent change in anti-fXa activity does not predict achievement of hemostatic efficacy. An AUC of 0.7 or higher is indicative of a relationship that is more useful in predicting hemostatic efficacy [27]. The Minimum Clinically Important Difference (MCID) of percent decrease in anti-fXa activity will be derived as the value that simultaneously maximizes sensitivity and specificity.

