5.5.2. Hemostatic Efficacy

For primary efficacy analysis, missing values (i.e., rated as Non-Evaluable due to administrative reasons) will be excluded from analysis. On the other hand, missing values due to non-administrative reason will be considered as treatment failure.

Non-evaluable for administrative reason is defined in the EAC Charter. The final decision regarding whether a patient is non-evaluable due to administrative or non-administrative reasons will be made by the EAC.

A sensitivity analysis will be performed with all patients rated as Non Evaluable classified as not reaching hemostatic efficacy.

5.5.3. **NIHSS**

Analysis will be performed only for the baseline and 12 hours post treatment. If the baseline or the 12-hour post-treatment NIHSS score is missing, the patient will be excluded from analysis.

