5.14. Secondary Efficacy Analysis

The secondary objective of the study is to assess the relationship between the change from baseline in anti-fXa activity and achievement of hemostatic efficacy in patients receiving an FXa inhibitor who have acute major bleeding and reduced FXa activity.

Analysis

A logistic regression model predicting the log-odds ratio of success of hemostatic efficacy (rated as "Excellent" or "Good"), with the anti-fXa level activity as a covariate will be used to determine the relationship between anti-fXa level and the clinical outcome.

A subset analysis on the Intracranial patients will be performed using a logistic regression with 2 additional covariates: the log of (the baseline ICH volume + 1), and an indicator variable for baseline Infratentorial involvement.

Anti-fXa Level Measurement

Hemostatic efficacy is achieved when the body has time to produce thrombin and a subsequent clot, thus the anti-fXa level during the first few hours after administration is more important than the decrease in anti-fXa level to predict the log-odds of success of hemostatic efficacy. Therefore, the on-treatment nadir value will be used in the analysis.

Standardization Across Inhibitors

The most power would be gained if it were possible to pool the data across all the anti-fXa inhibitors, however, anti-factor Xa activity levels cannot be combined in the same analysis due to the different bioavailability and pharmacokinetics of the individual FXa inhibitors, especially between the direct and indirect FXa inhibitors. An alternative way to use the activity level that would enable pooling the data is to convert the continuous measurements into a dichotomous variable indicating a level that has similar anticoagulant effects across the 4 different inhibitors.

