For the DOACs, current guidelines by the subcommittee on control of anticoagulation of the International Society on Thrombosis and Hemostasis (ISTH) and the French Working group on perioperative hemostasis (GIHP) recommend using a value of 30 ng/mL to determine if antidote administration should be considered.[4, 5] Unfortunately there is no similar threshold for the indirect anticoagulants, therefore the threshold for the Enoxaparin patients in the analysis will be the lower limit of detection (0.10 IU/mL). Sensitivity analyses excluding patients taking Enoxaparin will be performed as well, with (1) the log of anti-fXa at on-treatment Nadir as a covariate, and (2) the dichotomous variable for anti-fXa less than the threshold as a covariate.

A summary of the planned analyses is below:

Model	Population	Reduced Model covariates	Full Model covariates
1	Efficacy, excluding patients with Non-Evaluable Hemostatic Efficacy due to Admin reason	None (intercept only model)	Indicator variable for on- treatment Nadir anti-fXa level < threshold*
2	Same as (1) except exclude Enoxaparin patients also	None (intercept only model)	Indicator variable for on- treatment Nadir anti-fXa level < threshold*
3	Same as (1) except exclude Enoxaparin patients also	None (intercept only model)	Log of on-treatment Nadir anti-fXa level

4	Same as (1) except exclude non-ICH patients also	Log of (baseline ICH volume +1), Indicator	Reduced Model covariates plus Indicator variable for
	non-reri patients also	variable for Infratentorial	on- treatment Nadir anti-
		involvement	fXa level < threshold*

^{*}The threshold=30 ng/mL for Apixaban, Rivaroxaban and Edoxaban, and 0.10 IU/mL for Enoxaparin.

Descriptive statistics, odds ratios with the corresponding 95% confidence intervals, and p-values from the models will be presented. The Full Model will be compared to the Reduced Model with a Likelihood Ratio Test. The Reduced Model will be rejected in favor of the Full Model if the Likelihood Ratio Test p-value is <0.05.

The area under the receiver operating characteristic (AUC under ROC) with the 95% CI will be presented.

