All deaths will be assessed, and the causes of death adjudicated, by the EAC. Deaths due to cardiovascular causes (i.e., resulting from MI, sudden cardiac death, heart failure, stroke, CV procedures, CV hemorrhage, and other CV causes) will be classified as related to bleeding or non-hemorrhagic.

Kaplan-Meier curve for time to death will be presented by treatment by FXa inhibitor, and exanet dose, and and exanet manufacturing process. Patients who discontinue the study prior to Day 30 with an unknown survival assessment will be censored at the time of the last visit. Also, patients that completed the study (i.e., Day 30) will be censored at Day 30.

In addition, the proportion of patients that died during the 30 day follow-up with exact 95% CI will be presented for the overall safety population, by age category, region, FXa inhibitor, bleeding type, and exanet dose, and exanet manufacturing process, and by age deciles. In addition, the cause of death will be summarized.

The relationship between anti-fXa and 30-day mortality, will be analyzed (in the safety population), using a logistic regression model, with Age included as a covariate.

- 30-day mortality will define Death as Death at any time (including deaths recorded after Day 30). A sensitivity analysis defining Death as above (died during the 30 day followup) will be performed as well.
- Age will be entered into the model using a cubic spline transformation to best reflect the relationship with mortality.

- The Full Model will be compared to the Reduced Model with a Likelihood Ratio Test. The Reduced Model will be rejected in favor of the Full Model if the Likelihood Ratio Test p-value is <0.05.
 - Reduced Model: includes Age (with cubic spline transformation)
 - Full Model: includes Age (with cubic spline transformation) and an indicator variable for anti-fXa at on-treatment Nadir < threshold (where the threshold is 30 ng/mL for the DOACs, and 0.10 IU/mL for Enoxaparin).
- The area under the receiver operating characteristic (AUC under ROC) with the 95% CI will be presented for the Full Model.
- Descriptive statistics, odds ratios with the corresponding 95% confidence intervals, and p-values from the models will be presented also.

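### When neither on-treatment anti-fXa sample exists, the SAP's baseline-carried-forward nadir becomes the predictor in the hemostasis and mortality models and can bias the association they are meant to test

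*SAP*

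**What the plan says.** **Imputation.** SAP 5.5.1 applies when neither sample exists: "if both the EOB and EOI assessments are missing, the maximum change will be replaced with zero", and "the Nadir will be replaced with the baseline value using the Baseline Observation Carried Forward principle". It names no reason for missingness and no analysis to which it is confined. When one sample exists the rule does not apply: "If only one post-baseline sample is missing, the available sample (either EOB or EOI) will be used for the imputation".

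**Protocol counterpart.** Protocol 11.5.6 has a narrower rule, for the first primary endpoint only: "patients who do not have at least one anti-fXa activity level within the evaluation period for non-administrative reasons will have percent decrease imputed as 0.0" percent. SAP 5.17.2 does not list the difference among its changes.

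**Use as predictor.** SAP 4.4 takes the nadir for the secondary objective as described for the primary endpoint. SAP 5.14 confirms it: "Therefore, the on-treatment nadir value will be used in the analysis". Models 1, 2 and 4 use an indicator for a nadir below 30 ng/mL (apixaban, rivaroxaban, edoxaban) or 0.10 IU/mL (enoxaparin); model 3 uses the log of the nadir. SAP 5.16.3 enters "an indicator variable for anti-fXa at on-treatment Nadir < threshold" in the 30-day mortality model, fitted in the Safety Population with death at any time as the outcome.

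**Outcome coding.** Protocol 11.1 gives death as an example of being non-evaluable for clinical reasons. SAP 5.5.2 says "missing values due to non-administrative reason will be considered as treatment failure", and model 1 removes only administrative non-evaluables, so these patients stay in as failures.

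**The concern.** For the first primary endpoint, setting the change to zero is conservative. As a predictor, the same imputed value is not. One event, a death or collapse before any on-treatment sample, can fix both sides of the model: the patient is labelled not reversed and also has the bad outcome, with no post-dose anti-fXa value measured. Missingness that follows deterioration therefore pushes towards the hypothesis that reversal goes with hemostasis and survival. Missingness unrelated to outcome, such as a lost tube, passes through the same rule, mixes truly reversed patients into the not-reversed group and weakens any real association.

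The link between reversal and hemostasis is the study's only secondary efficacy objective. SAP 5.17.2 says that both association analyses are newly pre-specified in this version, and SAP 1.0 says that the analysis supports FDA and EMA submissions.

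No planned analysis would reveal the problem. Models 2 and 3 ("Same as (1) except exclude Enoxaparin patients also") change the inhibitors included or the form of the predictor, and model 4 changes the bleed type. The mortality sensitivity analysis changes only the definition of death. All keep the imputed nadirs.

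**Working it through.** **1. The plan's own figure.** With 162 patients, true rate 61% and null 50%, the exact two-sided 5% rule needs at least 94 successes. Its upper-tail error is 0.0246 and its power 0.805, so the stated 80% reproduces. The planned total also reproduces: 162/0.65 = 249.2, stated as 250. No design figure is given for the association models.

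**2. Where an imputed nadir falls.**

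| Inhibitor | Minimum baseline, Efficacy Population (SAP 5.2.2) | Reversed if nadir below (SAP 5.14) | Imputed patient |
|---|---|---|---|
| Apixaban, rivaroxaban | 75 ng/mL | 30 ng/mL | not reversed |
| Edoxaban | 40 ng/mL | 30 ng/mL | not reversed |
| Enoxaparin | 0.25 IU/mL | 0.10 IU/mL | not reversed |

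For enoxaparin the imputation does not change the code: SAP 5.5.1 sets values under 0.10 to 0.10 while the indicator needs a value under 0.10, so as written no enoxaparin patient can be reversed. In model 3 an imputed patient enters at the log of baseline.

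The Safety Population has no minimum baseline. In the mortality model a patient with a baseline already below threshold on a direct inhibitor is imputed as reversed, and a patient without a baseline has nothing to carry forward.

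**3. Inputs for size.**
- From the documents: 477 patients (SAP 1.0); about 30% below the evaluability cut-off and up to 5% non-evaluable (SAP 3.2), so N = 477 × 0.65 = 310 for hemostasis; failure rate 1 − 0.61 = 39%; at least 110 evaluable ICH patients.
- Assumed: share reversed 70% (range 50-85%), deaths 15% (range 10-20%), and k patients with neither sample, all with the bad outcome.

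**4. Spurious odds ratio with no true association.** Let q be the share reversed and p the bad-outcome rate. The k patients are added to the bad-outcome cell of the not-reversed group, so

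OR (bad outcome, not reversed vs reversed) = 1 + k / [(N − k)(1 − q)p].

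- Hemostasis, k=5: 305 × 0.3 × 0.39 = 35.7; OR = 1 + 5/35.7 = 1.14.
- Hemostasis, k=10: 300 × 0.3 × 0.39 = 35.1; OR = 1 + 10/35.1 = 1.28.
- Mortality, k=5: 472 × 0.3 × 0.15 = 21.2; OR = 1 + 5/21.2 = 1.24.
- Mortality, k=10: 467 × 0.3 × 0.15 = 21.0; OR = 1 + 10/21.0 = 1.48.

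**5. False-positive rate of the 5% likelihood ratio test** (40,000 simulated 2×2 tables per cell, 70% reversed):

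| k | Hemostasis, N=310 | ICH, N=110 | Mortality, N=477 |
|---|---|---|---|
| 0 | 5.1% | 5.1% | 5.0% |
| 1 | 5.1% | 5.4% | 5.3% |
| 2 | 5.4% | 6.0% | 5.8% |
| 5 | 7.8% | 12.6% | 11.1% |
| 10 | 16.5% | not run | 31.7% |

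Over 50-85% reversed, hemostasis gives 6.2-11.4% at k=5 and 10.0-31.5% at k=10. Over 50-85% reversed and 10-20% deaths, mortality gives 6.8-27.5% at k=5 and 13.4-80.6% at k=10. With k of 1 or 2 the overall models never exceed 7.6%. The age spline and the ICH covariates were not modelled.

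**6. Missingness unrelated to outcome.** With no true association the rate stays at about 5% and the OR at 1.00. With a true OR of 2.0 (N=310, 70% reversed), the estimate falls to 1.91 at k=10 and 1.84 at k=20.

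**The case against.** **Both samples must be missing.** Protocol Appendix A puts the first at, or within 30 minutes after, the end of a 15-30 minute bolus. A death must therefore come within about an hour of bolus start, or the first sample must be lost for another reason and the second as well. Patients with expected survival under one month, and ICH patients with a Glasgow score below 7, are excluded. The count may be very small. This stands: the documents give no count, and one or two such patients hardly matter in the overall models.

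**The mortality model is different.** A reader might infer that every unsampled patient is coded not reversed in both models. That is not so in the Safety Population, where a baseline below 30 ng/mL is imputed as reversed and works in the opposite direction. The share of such patients is not stated; SAP 3.2 gives only the roughly 30% below 75 ng/mL.

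**Larger effects need inputs from outside the documents.** With 320 evaluable patients, 18% failures, 75% reversed and 15 unsampled failures added, the OR is 1 + 15/(320 × 0.25 × 0.18) = 2.04, p = 0.011. Neither the 18% nor the 15 is in the documents. At the planned 39% failure rate the same setting gives 1 + 15/31.2 = 1.48, p = 0.108.

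**The stakes are limited.** SAP 5.7 treats secondary analyses as exploratory, and neither primary conclusion is affected. Listing 16.2.6.1 shows anti-fXa levels by patient, so these cases can be found. A listing does not remove them from the fitted models, however.

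**Conclusion.** The point holds in limited form. SAP 5.5.1 feeds an imputed nadir into the models of 5.14 and 5.16.3. In the hemostasis models that value always means not reversed; in the mortality model it does so unless baseline was already below threshold. The result can create or inflate an association, or dilute a real one, depending on why the samples are missing.

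The size rests on an unknown count. At 5 to 10 patients with neither sample, all with the bad outcome and 70% of the others reversed, the nominal 5% test rejects in about 8-17% of trials for hemostasis and 11-32% for mortality. The share reversed, the 15% mortality and the counts are assumptions.

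A reader might conclude that early deaths will produce the reported association, or that the bias can only favour the hypothesis. The documents support neither conclusion. They show only that the planned estimate could reflect the imputation and that no planned analysis would tell.

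**What to change.** - Keep the baseline-carried-forward rule for the first primary endpoint, and say in SAP 5.5.1 that it is confined to that endpoint.
- Fit the models in 5.14 and 5.16.3 on patients with at least one observed EOB or EOI value. For mortality, restrict to patients alive at end of infusion; excluding unsampled patients alone would still select on survival to sampling without saying so.
- Report the number of patients with neither sample, the reasons and their outcomes, and show the imputed version only as a sensitivity analysis.
- State in the SAP that its imputation trigger for the first primary endpoint is broader than that of Protocol 11.5.6. Narrowing it to match would drop a conservative zero-change value for administrative missingness and is not needed.

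The cost is SAP wording, a few patients fewer in exploratory models, and results that apply only to patients who survive to sampling. No new data are needed. With those patients left out (k=0), the simulated false-positive rate returns to about 5% (4.9-5.2% in the overall models, 5.1-5.8% in the ICH model).

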5.5.2. Hemostatic Efficacy

For primary efficacy analysis, missing values (i.e., rated as Non-Evaluable due to administrative reasons) will be excluded from analysis. On the other hand, missing values due to non-administrative reason will be considered as treatment failure.

Non-evaluable for administrative reason is defined in the EAC Charter. The final decision regarding whether a patient is non-evaluable due to administrative or non-administrative reasons will be made by the EAC.

A sensitivity analysis will be performed with all patients rated as Non Evaluable classified as not reaching hemostatic efficacy.

5.5.3. **NIHSS**

Analysis will be performed only for the baseline and 12 hours post treatment. If the baseline or the 12-hour post-treatment NIHSS score is missing, the patient will be excluded from analysis.

5.5.4. Ambiguous Values

In the case where a variable is recorded as "> x", " \geq x", " \leq x", " \leq x", then for analysis purposes a value of x will be taken. Where a range of values is quoted the midpoint of the range

will be taken. In the case where a patient records more than one score for any particular measure, the worst of the recorded scores will be taken for analysis purposes. In all cases, sites will be queried first to determine whether a more precise value is available.

5.6. Multiple Investigator Sites

Sites will be grouped according to the Region as North America and Europe.

5.7. Multiple Comparisons/Multiplicity

No adjustment is planned for multiple secondary endpoints. Secondary analyses and secondary outcomes will be treated as 'exploratory' analyses to assess the consistency of the primary efficacy analysis.

5.8. Use of Efficacy Subset

As defined in the previous section, primary analyses will be performed using the efficacy analysis population. In addition, primary efficacy analysis will be performed by sex, age category, country, bleeding type, FXa Inhibitor, and exanet manufacturing process, and and exanet dose.

5.9. Data Derivation

- The following derivation rules will apply: unless missing data is imputed using the
 imputation methods described above, all tabulations involving change from baseline data
 will only include subjects with cohort data i.e. with data at baseline and at follow-up.
 Change from baseline will be calculated as follow-up values minus baseline value.
 Percentage changes from baseline will be rounded to 1 decimal place.
- For analysis purposes, 1 month = 30 days and duration in months will be rounded to 1 decimal place.
- Any derived data recorded in hours will be rounded to 1 decimal place.
- All calculation of length of time, including age, should be performed using SAS function to account for leap year.
- Height in inches will be converted to centimeters by multiplying by 2.54 and rounding to the nearest integer.
- Weight in lbs will be converted to kg by dividing by 2.2046 and rounding to 1 decimal place.
- Body mass index (BMI) will be calculated as weight (kg) / (height (cm)/100)² rounded to 1 decimal place.
- Temperature in Fahrenheit will be converted to Celsius by subtracting 32 and dividing by 1.8.

- Hemoglobin in g/L will be converted to mmol/L by multiplying by 0.06206 and rounding to 2 decimal places.
- To convert from g/dL to g/L multiply by 10.
- To convert from mg/dL to g/L multiply by 0.01 and round to 2 decimal places.
- To convert from mEq/L to mmol/L multiply by 1.
- To convert from µkat/L to U/L multiply by 1.
- For white blood cell and platelet count then $10^9/L = 10^3/\text{mm}^3$.
- For each white blood cell differential (Neutrophils, Lymphocytes, Monocytes, Eosinophils, Basophils) to convert from % to 10⁹/L by multiplying the value by the WBC (10⁹/L) and dividing by 100 and rounding to 1 decimal place.
- For creatinine to convert from μmol/L to mg/dL divide by 88.4173 and round to 1 decimal place.
- For serum glucose to convert from mmol/L to mg/dL divide by 0.0555 and round to 1 decimal place.
- For blood urea nitrogen to convert from mmol/L to mg/dL divide by 0.3651 and round to 1 decimal place.
- For total and direct bilirubin to convert from μmol/L to mg/dL to μmol/L divide by 17.0999 and round to 1 decimal place.
- For calcium to convert from mmol/L to mg/dL divide by 0.2495 and round to 2 decimal places.
- For phosphorous to convert from mmol/L to mg/dL divide by 0.3229 and round to 2 decimal places.
- For plasma concentrations that are lower than lower level of quantification (LLOQ) then
 the value will be taken as LLOQ threshold value.
- For plasma concentrations that are higher than the upper level of quantification (ULOQ) then the value will be taken as ULOQ threshold value.

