4.2. Demographic and Baseline Characteristics

4.2.1. Demographic Variables

- Protocol Version to which subject was enrolled
- Age (years)
- Age Category: < 65, 65 75, > 75 years
- Age Deciles: < 19 years; 19 29, 30 39; 40 -49; 50 59, 60 -69, 70 79, 80 -89, 90 99 years
- Sex (Male, Female)

- Ethnicity (Hispanic or Latino, Not Hispanic or Latino, Not responded, Unknown)
- Primary Race (American Indian or Alaska Native, Asian, Black or African American, Native Hawaiian or Other Pacific Islander, White, Other). For patients enrolled in Japan with Japanese ancestry, the race should be designated as Japanese.
- Height (cm)
- Weight (kg)
- BMI (kg/m²)
- Estimated glomerular filtration rate (eGFR): eGFR will be estimated in mL/min using the Cockcroft and Gault equation as follows:
 - o If patient is "Female" eGFR = 0.85 * (140- AGE) * WEIGHT / (AVAL * 72)
 - If patient is "Male" eGFR = (140- AGE) * WEIGHT / (AVAL * 72)
 - AVAL = creatinine at baseline, pre-andexanet dosing
- Bleeding Type: Bleeding type will be defined based on the screening evaluation
 performed by the investigator (i.e., primary bleeding assessment, CRF #208) and on the
 adjudication. The adjudicated bleeding entry criteria is defined by the EAC as presented
 in CRF #120. Investigator assessment is defined as follows:
 - o GI if primary bleed is GI,
 - o ICH if primary bleed is Intracranial Hemorrhage,
 - Other if primary bleed is Urinary, Muscular/skeletal non-visible, other non-visible, or Visible.
 - Multiple primary bleed types should be concatenated and separated by a semi colon.
- Time from Baseline Scan to Andexanet Treatment: Time from baseline scan to start of andexanet is calculated as the difference in hours from time of baseline scan (CRF #160, screening CRF) to the start of andexanet (CRF #010/210, bolus start).
- Time from Bleeding to Andexanet Treatment: Time from bleeding to andexanet treatment is calculated as the difference in hours from the onset of primary bleeding (CRF #008/208) to start of andexanet treatment (CRF #010/210, bolus start).
- Time from Bleeding to Baseline Scan: Time from bleeding to scan is calculated as the difference in hours from onset of primary bleeding (CRF #008/208) to the time of baseline scan (CRF #160, screening CRF).

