4.2.8. Coagulation and Biochemistry within 3 hours of Bolus

- INR
- Prothrombin time (sec)
- Fibrinogen (g/L)
- Potassium (mmol/L)
- Creatinine (mg/dL)
- Creatinine Clearance By Cockcroft-Gault (ml/min)
- ALT (U/L)
- AST (U/L)
- Total Bilirubin (µmol/L)
- Alkaline Phosphatase (U/L)
- Direct Bilirubin (µmol/L)

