5.13.1.2. Exploratory Analysis

Consistency of efficacy across important subgroups will be investigated. Analysis will be performed for the efficacy population. The two primary endpoints will be summarized for the following subgroups:

- Sex (Male, Female)
- Race (any race with at least 5 members, all other races combined)
- Age (< 65 years, 65–75 years, >75 years)
- FXa inhibitor (apixaban, rivaroxaban, edoxaban, enoxaparin)
- Bleed type (GI, ICH, Other)
- Dose of andexanet (low dose [400 mg bolus + 480 mg infusion], high dose [800 mg bolus plus 960 mg infusion])
- Region (North America, Europe, and Japan)
- Renal function (eGFR < 50 mL/min, eGFR ≥ 50 mL/min)

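### Two laboratory conversion rules in SAP 5.9 are wrong: microkatal/L to U/L uses a factor of 1 instead of 60, and the bilirubin rule divides away from the reporting unit

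*SAP*

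**What the plan says.** SAP 5.9 lists the unit conversions for laboratory data. Four of them matter here.

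- **Enzymes.** Values in microkatal/L are converted "to U/L multiply by 1". SAP 4.2.8 lists ALT, AST and alkaline phosphatase in U/L.
- **Bilirubin (total and direct).** The rule describes its direction as micromol/L to mg/dL and then to micromol/L again, and the operation is "divide by 17.0999 and round to 1 decimal place". SAP 4.2.8 lists "Total Bilirubin" and direct bilirubin in micromol/L.
- **Creatinine.** Values in micromol/L are converted "to mg/dL divide by 88.4173 and round to 1 decimal place", and 4.2.8 lists "Creatinine (mg/dL") as the reporting unit. The Cockcroft-Gault formula in SAP 4.2.1 uses "AVAL = creatinine at baseline, pre-andexanet dosing" and does not say whether that value is rounded. SAP 5.13.1.2 uses the result for one exploratory subgroup: "Renal function (eGFR < 50 mL/min, eGFR ≥ 50 mL/min").
- **Urea nitrogen.** Values in mmol/L are divided by 0.3651 to give mg/dL.

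Protocol 10.2.3 places routine chemistry at local laboratories, and the synopsis allows up to 120 sites in North America, Europe and Japan. Protocol Appendix A schedules chemistry once, before the bolus.

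**The concern.** A conversion rule in a SAP is an instruction that a programmer is expected to follow literally. The enzyme rule is a complete sentence with a definite factor, and that factor contradicts the definition of the unit. The bilirubin rule cannot be followed in any way that yields the unit in which the SAP reports bilirubin. With local laboratories in three regions, mixed units are plausible, and the presence of these rules shows that the sponsor provided for them.

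At stake is the baseline description of liver function. A clearly raised enzyme value could print as a very low one, and bilirubin values in two units could sit under one label. SAP 1.0 says the analysis supports marketing submissions to FDA and EMA, so these tables will be read by people who cannot see the source unit.

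**Working it through.** **1. Enzymes.** The SAP's factor is 1. The definition gives:

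- 1 microkatal = 1 micromol per second = 60 micromol per minute = 60 U, so microkatal/L to U/L is × 60.
- 0.67 microkatal/L: the SAP rule gives 0.67 U/L; the definition gives 0.67 × 60 = 40.2 U/L.
- 5.0 microkatal/L: the SAP rule gives 5.0 U/L; the definition gives 300 U/L.

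The rule acts only on values received in microkatal/L, so every value it touches is 60-fold low and every value already in U/L is unaffected. The line just above it in 5.9, mEq/L to mmol/L with a factor of 1, suggests that the factor was carried down. That is an inference.

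**2. Bilirubin.** The size of the factor is right: 10,000 / 584.66 (molar mass) = 17.10. The problem is the direction.

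- Input in micromol/L: 20 / 17.0999 = 1.2. That is the correct number in mg/dL, but under the micromol/L label of 4.2.8 it is 17-fold low.
- Input in mg/dL: the needed value is 1.2 × 17.0999 = 20.5 micromol/L. Dividing gives 0.07, printed as 0.1. Before rounding the error is 17.0999² = 292-fold.

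**3. Creatinine and eGFR.** The factor is right: 10,000 / 113.12 = 88.40, against 88.4173 in the SAP. Only the rounding to 0.1 mg/dL is open, and only if the rounded value enters the formula (140 − age) × weight / (72 × creatinine), multiplied by 0.85 for women.

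- Man aged 80, 62 kg, 92 micromol/L: creatinine 1.0405, eGFR = 3720 / (72 × 1.0405) = 49.7. Rounded to 1.0, eGFR = 51.7. He moves above 50.
- Man aged 77, 61 kg, 93 micromol/L: creatinine 1.0518, eGFR = 50.7. Rounded to 1.1, eGFR = 48.5. He moves below 50.

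The documents give no distribution of age, weight or creatinine, so four populations were assumed and simulated (2 million patients each, 47% female, all creatinine in whole micromol/L, log-normal creatinine):

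| Age, mean (SD) | Weight kg, mean (SD) | Median creatinine mg/dL (log-SD) | Change group |
|---|---|---|---|
| 77 (11) | 77 (18) | 1.0 (0.30) | 1.9% |
| 77 (11) | 75 (18) | 1.1 (0.35) | 1.9% |
| 80 (8) | 60 (12) | 0.9 (0.35) | 2.6% |
| 65 (12) | 85 (18) | 0.9 (0.30) | 0.8% |

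Moves in the two directions are about equal, and nearly all involve a true eGFR of about 47 to 53. Applied to the 477 patients of SAP 1.0, 0.8% to 2.6% is about 4 to 12, but only if every creatinine arrived in micromol/L and the rounded value were used.

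**4. Urea nitrogen.** From two nitrogen atoms, 10 / 28.0134 = 0.357. The SAP's 0.3651 makes converted values 0.357 / 0.3651 = 0.978 of the true value, or 2.2% low.

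The factors for glucose, calcium, phosphorus and hemoglobin agree with molar mass.

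**5. Where the values go.** The outputs named in the SAP are baseline: Table 14.1.1.16 and Listing 16.2.4.5 for biochemistry. SAP 5.16.6 plans change-from-baseline statistics for hematology only.

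**The case against.** The strongest reply is that the practical effect may be nothing. The documents do not say that any site reports enzymes in microkatal/L. If none does, the wrong factor is never applied. Even if some do, chemistry is scheduled only before the bolus, the values are baseline descriptors, and no primary or secondary endpoint uses them. Classification as low, normal or high in SAP 5.16.6 uses each laboratory's own ranges, which is safe if value and range share a unit. The bilirubin line is plainly garbled: a programmer who divided micromol/L and labelled the output mg/dL would have correct numbers and only a label that differs from 4.2.8.

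Most of this stands, and it limits the reach of the point. It does not make the two rules right. The SAP does not say that value and range are kept in one unit, and a rule that works only when a programmer departs from it needs correcting.

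A reader might infer more: that enzymes are 60-fold low across the trial, or that the renal subgroups are misassigned. The documents support neither. The first holds only for results received in microkatal/L. For the second, the creatinine factor is correct, the SAP does not say that the rounded value enters eGFR, and at most a small fraction of patients close to 50 mL/min could move. The renal split is also an exploratory summary, and it is absent from the minimum subgroup list in protocol 11.8. Nor should urea nitrogen be given weight: it is not among the biochemistry variables of SAP 4.2.8.

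**Conclusion.** The point holds for two rules. The enzyme factor is wrong by definition, with a 60-fold error in every value to which it is applied. The bilirubin rule is ambiguous in direction and wrong for the stated reporting unit under either reading: 17-fold for micromol/L input and about 292-fold for mg/dL input. These sizes rest on unit definitions and molar mass, not on assumptions about the trial.

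How many results are affected is unknown, because the documents do not give the units that sites use. The consequence is limited to baseline chemistry tables and listings. No primary endpoint is affected.

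The creatinine rounding is a minor clarification. The 0.8% to 2.6% depends on the assumed populations, applies only to patients with creatinine reported in micromol/L, and requires that the rounded value be used. The urea nitrogen divisor is a 2.2% error that matters only if urea nitrogen is reported.

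**What to change.** In SAP 5.9:

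- Microkatal/L to U/L: multiply by 60.
- Bilirubin: mg/dL to micromol/L, multiply by 17.0999; leave values already in micromol/L unchanged.
- State that each value and its laboratory normal range are kept in, or converted to, the same unit. This matters more once the enzyme factor is corrected: a value multiplied by 60 and compared with an unconverted range would be flagged high.

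Minor additions: state in SAP 4.2.1 that eGFR uses unrounded creatinine, with rounding for display only; and, if urea nitrogen is reported, change its divisor from 0.3651 to 0.357.

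The cost is a few lines of SAP text and a rerun of the laboratory derivations. There is no scientific trade-off. A count of source units by site in the laboratory data would show at once whether any tabulated value changes.
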